8.2.3.2. Adverse Events by Maximum Grade or Intensity

A summary of AEs by grade or intensity will be presented in a table. The grade or intensity that will be presented represents the most extreme grade or intensity captured on the CRF page. The possible grades or intensities are “Not applicable”, “Mild or Grade 1”, “Moderate or Grade 2”, “Severe or Grade 3” and “Grade 4”. In the grade or intensity table, if a patient reported multiple occurrences of the same AE, only the most severe will be presented. AEs that are missing grade or intensity will be presented in tables as “Grade 4” but will be presented in the data listing with a missing grade or intensity.

The AE will be summarized by maternal, fetal and neonatal events, separately.

8.2.3.3. Most Common Adverse Events

A summary of most common on-treatment adverse events (>2% incidence rate among retosiban and atosiban group) by treatment will be produced.

Most common AEs will be reported in the similar manner as all AEs.

The AE will be summarized by maternal, fetal and neonatal events, separately.

8.2.3.4. Serious Adverse Events

The seriousness of an AE should be assessed by the Investigator independently from the severity of the AE. A serious AE (SAE) is defined as any untoward medical occurrence that at any dose results in death, is life-threatening, requires hospitalization or prolongation of existing hospitalization, results in disability/incapacity, is a congenital anomaly/birth defect, or is possible of drug-induced liver injury with hyperbilirubinemia.

Important medical events that may not result in death, be life-threatening, or require hospitalization may be considered SAEs when, based upon medical judgment, they may jeopardize the subject and may require medical or surgical intervention to prevent one of the outcomes listed above.

SAEs will be reported in the similar manner as all AEs. A listing of SAEs will be provided. Also, the above summary will be produced by subgroups as defined in Section **Error! Reference source not found.**

The SAEs will be summarized by maternal, fetal and neonatal events, separately. Also, the maternal SAEs by treatment phase (on-treatment, post-treatment) defined in Section 11.3.3 will be summarized.

8.2.3.5. Adverse Events Leading to Treatment Discontinuation

A listing of all AEs leading to permanent discontinuation of study drug and/or withdrawal from the study will be produced if applicable.

The AEs leading to permanent discontinuation will be summarized only for maternal events if applicable.

8.2.3.6. Adverse Events of Special Interest

Adverse Events of Special Interest (AESIs) are AEs potentially related to treatment administration (direct or indirect) and are of special interest for evaluating and characterizing the outcomes of women, fetuses, and neonates participating in this study.

AESIs will be reported in the similar manner as all AEs. A listing of AESIs will be provided. Also, the above summary will be produced by subgroups defined in Section **Error! Reference source not found.**

The AESIs will be summarized by maternal, fetal and neonatal events, separately.

Maternal, fetal and neonatal AESIs are as follows:

Maternal AESIs:

- Maternal death
- Chorioamnionitis and its complications
 - Clinical chorioamnionitis, PPROM, endomyometritis, wound infection, pelvic abscess, bacteremia, septic shock, disseminated intravascular coagulation, and adult RDS
- Placental abruption
- Postpartum hemorrhage - postpartum hemorrhage and/or retained placenta (as assessed by AEs, time to expulsion of the placenta, assessment of uterotonic agents used, and change in hemoglobin from baseline value to 24 to 48 hours post-delivery adjusting for mode of delivery)
- Pulmonary edema

Fetal AESIs:

- Intrauterine fetal demise
- Category II or III fetal heart rate tracing (defined according to ACOG Practice Bulletin 106 [ACOG, 2009])
- Fetal inflammatory response syndrome characterized by cord blood interleukin-6 >11 pg/mL, funisitis, or chorionic vasculitis

Neonatal AESIs:

- Neonatal death
- Asphyxia
- Infections (early onset neonatal sepsis, septic shock, pneumonia, meningitis)
- RDS
- Hypotension
- IVH/periventricular leukomalacia
- Bronchopulmonary dysplasia
- Neonatal acidosis
- Hyperbilirubinemia
- Neonatal enterocolitis
- Hypoxic ischemic encephalopathy

8.2.3.7. Disease-Related Events and/or Disease-Related Outcomes Not Qualifying as SAEs

Maternal and neonatal disease-related events (DREs) described below will be reported in a similar manner as all AEs. A listing of DREs will be provided. Also, the above summary will be produced by subgroups defined in Section **Error! Reference source not found.**

The DREs will be summarized by maternal and neonatal events, separately.

The following DREs are common maternal events during pregnancy, labor, and delivery:

- Signs and symptoms of labor discomfort (e.g., cramping, backache, muscle aches, nausea)

- Subsequent episodes of preterm labor (even if hospitalization is required) unless 1 of the conditions listed at the end of Protocol Section 6.3.7.2 applies
- Hospitalization for delivery, unless prolonged or 1 of the conditions listed at the end of Protocol Section 6.3.7.2 applies Signs and symptoms of labor discomfort (e.g., cramping, backache, muscle aches, nausea)

The following DREs are common neonatal events related to prematurity and can be serious or life threatening:

- Lungs and respiratory system
 - Apnea (severe)
 - Respiratory failure due to fatigue, hypoxia, or air leak from alveolar injury
- Cardiovascular
 - Patent ductus arteriosus
 - Bradycardia
- Neurological
 - Ventriculomegaly
 - Cerebellar hemorrhage
 - Hydrocephalus other than congenital
- Gastrointestinal
 - Gastroesophageal reflux
 - Aspiration pneumonia
- Hematologic
 - Anemia (severe)
- Vision
 - Retinopathy of prematurity (all stages)
- Auditory
 - Hearing disorder
- Other

- Temperature instability
- Hypoglycemia

These events will be recorded on the DRE page in the maternal or neonatal eCRFs. These DREs will be monitored by the IDMC and internal safety review committee. However, if one or all of the following conditions apply, then the event should be reported as an AE/SAE using the standard process:

- The event is, in the investigator's opinion, of greater intensity, frequency, or duration than expected for the individual subject,
- The investigator considers that there is a reasonable possibility that the event was related to treatment with the IP, or
- An event defined as a disease-related neonatal event is reported in an infant born ≥ 37 completed weeks.

If any of the above conditions are met, then record the event on the SAE page rather than the DRE page and report promptly.

8.2.3.8. Death

Deaths will be reported in the similar manner as all AEs. If applicable, a listing of death will be provided by maternal, fetal or neonatal events, separately.

8.2.4. Health Outcome

8.2.4.1. Neonatal Health Care

Neonatal health care will be summarized using Neonatal Safety Population.

Descriptive statistics will be summarized for length of Intensive Care Unit (ICU) or Neonatal Intensive Care Unit (NICU) in days for neonates at birth by treatment.

The following variables will be summarized with number and percentage for neonates with hospital unit utilization at birth by treatment:

- Total number of neonates with hospital unit utilization at birth
- Hospital unit type (Accident and emergency (observation), General ward, High dependency unit/step down unit, Intensive care unit, etc.)
- ICU or NICU admissions (yes, no)
- Number of ICU or NICU admissions (1, 2, 3, >3)
- Length of hospital stay in days (≤ 3 , $> 3 - \leq 7$, > 7).

RR and 95% CI, OR and 95% CI, and corresponding p-value for ICU or NICU admissions will be provided. ICU or NICU admissions will be analyzed in a similar fashion to the neonatal composite analysis in Section 8.1.2.

A listing of all data available for neonatal health care utilization both at birth and readmission will be provided for Neonatal Safety population.

8.2.4.2. Maternal Health Care

Maternal health care will be summarized using Maternal Safety Population.

Descriptive statistics will be summarized for cumulative length of hospital stays in days for pre-term labor related hospital admission and hospital admission at delivery by delivery status (Pre-Term Delivery (<37 Weeks of GA), Term Delivery \geq 37 Weeks of GA)) by treatment. The following variables will be summarized with number and percentage for pre-term labor related hospital admission by treatment:

- Total number of subjects with pre-term labor related hospital admission
- Number of hospital admissions (1, 2, 3, >3)
- Cumulative length of hospital stay in days (≤ 3 , $>3-\leq 7$, >7)
- Hospital unit type (Accident and emergency (observation), General ward, High dependency unit/step down unit, Intensive care unit, etc.).

The following variables will be summarized with number and percentage for hospital admission at delivery by delivery status (Pre-Term Delivery (<37 Weeks of GA), Term Delivery \geq 37 Weeks of GA)) by treatment:

- Number of subjects with hospital admission at delivery;
- Cumulative length of hospital stay in days (≤ 3 , $>3-\leq 7$, >7);
- Maternal hospital unit type (Accident and emergency (observation), General ward, High dependency unit/step down unit, Intensive care unit, etc.).

A listing of all data available for maternal pre-term labor related and at delivery health care resource utilization will be provided for maternal safety population.

8.2.5. Clinical Laboratory

Summaries for hematology and chemistry parameters will be performed using the Maternal Safety Population.

Summary tables presenting observed values and changes from baseline will be presented for clinical laboratory tests with numeric values by treatment group. Changes from baseline to each scheduled post-baseline visit will be presented.

The number and percentages of subjects with laboratory values outside the reference ranges will be summarized by treatment groups (hematology).

The subjects with laboratory values outside the reference ranges (hematology and chemistry) will be listed. The criteria for laboratory values outside of normal ranges are detailed in Appendix 11.8.1. If there are only the lower or upper ranges, only the lower or upper changes will be calculated for direction of interests.

8.2.6. Vital Signs

8.2.6.1. Maternal Vital Signs

Summaries for maternal vital signs will be performed using the Maternal Safety Population

Summary tables will be presented for vital sign data including weight (kg), height (cm), systolic blood pressure (mmHg), diastolic blood pressure (mmHg), temperature (°C), heart rate (beats/min), and respiration rate (breaths/minute), by treatment group.

Observed results at each scheduled timepoint (Screening, Inpatient Randomized Treatment Phase (15 to 30 minutes, 4 to 8 hours, and 20 to 24 hours after the start of the infusion, at the end of the infusion), and at the face-to-face post-infusion assessment visit), will be presented. Changes from baseline to each scheduled post-baseline visit will be presented.

All maternal vital sign data below and above normal ranges will be presented in a listing. The criteria for vital signs values with potential clinical importance are detailed in Appendix 11.8.2.

8.2.6.2. Fetal Heart Rate

Summaries for fetal heart rate will be performed using the Maternal Safety Population.

A table will summarize categorical fetal heart rate results by treatment group during treatment phase and post-treatment phase. Categories to be presented are Category I, II and III based on ACOG guidelines [ACOG, 2009].

All fetal heart rate data by subject will be presented in a listing.

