1.2. Rationale

This study is being conducted based on the results of the OTA10256 study that demonstrated significantly longer time to delivery. Specifically, OTA105256 was a Phase II study of retosiban for the treatment of spontaneous preterm labor in women with singleton pregnancies and intact membranes. This study initially examined the pharmacokinetics, dose response, and safety of retosiban in women for whom the gestational age (GA) was restricted to $34^{0/7}$ and $35^{6/7}$ weeks. Retosiban was given intravenously with the loading dose and infusion rate increased in a stepwise fashion every 3 hours to achieve target plasma concentrations. Alternate tocolytic drugs were not permitted during the study's IV infusion phase. Twenty-nine adult subjects (ages 18 to 37 years) were enrolled into Parts A and B. An interim analysis, indicating retosiban suppressed contractions and prolonged pregnancy, resulted in an additional cohort (Part C with a lowered GA to $30^{0/7}$ weeks) to evaluate retosiban in a clinical population and setting more consistent with current practice guidelines for tocolytic use. Sixty-four adult subjects (ages 18 to 41 years) were enrolled, randomly assigned to treatment, and dosed in Part C.

Data from Study OTA105256 found that retosiban treatment, at a dosing regimen of 6-mg load over 5 minutes, then 6 to 12 mg/hour based on response, was associated with a higher proportion of females achieving uterine quiescence and a significant difference in time to delivery and reduction in preterm births. Uterine quiescence was defined as 4 or fewer contractions per hour with no change in cervical dilation greater than 1 cm. Using partial informative priors, which partially weighted the Part A/B response rates for retosiban and placebo, the posterior mean response rate within the initial 6 hours of treatment was 62% in the retosiban group compared with 41% in the placebo group. The posterior relative risk of achieving quiescence was 1.53 (95% confidence interval [CI]: 0.98, 2.48).

Retosiban treatment was also associated with a significant difference in time to delivery and births prior to 37 weeks of gestation. The posterior mean difference in time to delivery was 8.2 days relative to placebo (95% CI: 2.7, 13.74). The percent of preterm births in the retosiban and placebo groups was 18.7% and 47.2%, respectively. The posterior relative risk for preterm birth in the retosiban group was 0.38 (95% CI: 0.15, 0.81).

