19. Electronic fetal monitoring is required for a minimum of 6 hours from the start of the infusion or from the start of a dose increase. As long as the fetal heart rate pattern is consistently reassuring throughout the required 6-hour duration of monitoring and the contraction frequency is ≤ 2 in a 30-minute window within the last hour of monitoring, continuous monitoring may be discontinued and nonstress tests initiated at a minimum of every 8 hours and as needed. Electronic fetal monitoring, including the fetal heart rate and fetal heart rate category, will be recorded in the eCRF with maternal vital signs. Any fetal heart rate assessment of Category II or III will be reported as an AE of special interest on a specified eCRF (details in Section 6.3.12.3).
20. If the subject has not delivered at the end of the Inpatient Randomized Treatment Phase, fetal heart rate (fetal Doppler heart rate or cardiotocography are both acceptable) will be recorded at the face-to-face post-infusion assessment visit. Any fetal heart rate assessment of Category II or III will be reported as an AE of special interest on a specified eCRF (details in Section 6.3.12.3).
21. During the Delivery Phase, fetal heart rate just prior to delivery will be collected, if available, from review of delivery records. Any fetal heart rate assessment of Category II or III will be reported as an AE of special interest on a specified eCRF (details in Section 6.3.12.3).
22. Maternal and neonatal health care resource use may include, but is not limited to, neonatal complications requiring intensive or specialized care, neonatal hospital readmission, and neonatal ambulatory surgery.
23. PK samples will be taken at the following sampling windows (relative to the start of the infusion): 2 to 4 hours, 10 to 14 hours, 22 to 26 hours, and 48 to 54 hours. In addition, a PK sample should be taken at the onset of any maternal or fetal SAE that occurs within 12 hours after completion or discontinuation of IP. A maternal blood sample should be collected at the same time as the cord blood sample (see Section 6.5.1) if the sample time does not already coincide with one of the PK sampling windows.
24. In subjects who deliver at an investigative center within 12 hours following completion or discontinuation of the IP, the cord blood sample will also be divided for PK analysis as well as genetic (if additional consent is provided; see [Appendix 1](#)) and biomarker analyses.

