6.3.12.3. Electronic Fetal Monitoring

Electronic fetal monitoring is required for a minimum of 6 hours from the start of the infusion or from the start of a dose increase if the following are confirmed during monitoring:

- The fetal heart rate pattern is consistently reassuring throughout the required minimum 6-hour duration of monitoring
- The contraction frequency is ≤ 2 in a 30-minute window within the last hour of monitoring.

A reassuring nonstress test (defined as meeting Category I criterion), accounting for GA expectations, is required at a minimum of every 8 hours and as needed. An additional 6 hours of electronic fetal monitoring will be required for dose interruptions that are sufficiently long as to require an additional infusion bolus of the IP.

Electronic fetal monitoring, including the fetal heart rate and fetal heart rate category, should be recorded in the eCRF at approximately the same time that maternal vital sign measurements are collected (Section 6.3.12.2). The electronic fetal heart rate tracing (paper or electronic) must be archived and retained in site records. Fetal heart rate (fetal Doppler heart rate or cardiotocography are both acceptable) will be recorded at the face-to-face post-infusion assessment visit if the subject remains undelivered. During the Delivery Phase, fetal heart rate just prior to delivery will be summarized, if available, from review of delivery records. Any fetal heart rate assessment of Category II or III according to the following criteria and based on ACOG guidelines [ACOG, 2009] will be reported as an AE of special interest on a specified eCRF in addition to the corresponding AE or SAE eCRF:

Category I fetal heart rate tracings include all of the following:

- Baseline rate: 110 to 160 beats per minute
- Baseline fetal heart rate variability: moderate
- Late or variable decelerations: absent
- Early decelerations: present or absent
- Accelerations: present or absent

Category II fetal heart rate tracings include all fetal heart rate tracings not categorized as Category I or III. Category II tracings may represent an appreciable fraction of those

encountered in clinical care. Examples of Category II fetal heart rate tracings include any of the following:

- Baseline rate
 - Bradycardia not accompanied by absent baseline variability
 - Tachycardia
- Baseline fetal heart rate variability
 - Minimal baseline variability
 - Absent baseline variability with no recurrent decelerations

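### Percentages of women with Category II/III fetal heart rate events can be distorted because, after 6 hours, time on the monitor depends on contraction response; a display at scheduled readings common to both arms should stand beside them

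*SAP*

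**What the plan says.** **Monitoring rule.** Protocol 6.3.12.3 states: "Electronic fetal monitoring is required for a minimum of 6 hours from the start of the infusion or from the start of a dose increase". Two conditions govern stopping. The tracing must have stayed reassuring for the whole 6 hours or more. For contractions, the condition reads: "The contraction frequency is ≤ 2 in a 30-minute window within the last hour of monitoring". Protocol Table 5, footnote 19, adds that once contractions have settled "within the last hour of monitoring, continuous monitoring may be discontinued and nonstress tests initiated at a minimum of every 8 hours".

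**What is recorded.** Footnote 19 and Protocol 6.3.12.3 have the category entered in the eCRF with the maternal vital signs. Protocol 6.3.12.2 sets those at 15–30 minutes, 4–8 hours, 20–24 hours and end of infusion, plus any dose change and as medically warranted. Any Category II or III assessment becomes an event of special interest. Footnote 21 applies the same rule to the tracing just before delivery, if available. At the follow-up visit, "fetal heart rate (fetal Doppler heart rate or cardiotocography are both acceptable) will be recorded at the face-to-face post-infusion assessment visit".

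**Analysis.** SAP 8.2.3.6 lists "Category II or III fetal heart rate tracing (defined according to ACOG Practice Bulletin 106" among the fetal events of special interest and reports these like all adverse events. Under SAP 8.2.3.1 that means number and percentage of subjects with at least one event. Tables 3.171 and 3.172 use the Maternal Safety Population, that is, dosed women. For Table 3.424, SAP 8.2.6.2 says: "A table will summarize categorical fetal heart rate results by treatment group during treatment phase and post-treatment phase". Neither document adjusts for time monitored.

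**The concern.** A Category II or III pattern can be found only while someone is looking. All women on treatment and undelivered are monitored for the first 6 hours. After that, women whose contractions settle may come off the monitor and move to intermittent nonstress tests. Women whose contractions persist stay on. A dose increase for inadequate response restarts the 6 hours and adds a category record. Protocol 3.2.1.1 reports that 40% of Phase II Part C subjects needed the higher rate, so this will not be rare.

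The intensity of looking is thus a post-randomization variable tied to tocolytic response. Comparing plain percentages of dosed women mixes the true event rate with the time observed. Describing fetal safety against atosiban is a secondary objective, and with no formal safety test planned (Protocol 8.3.5.2) readers will judge these percentages by eye.

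**Working it through.** The documents give no rate, event count or power for Category II/III tracings, so there is no figure to reproduce. The check asks what the tables would show if the true event rate were the same in both arms.

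**Input from the documents.** The closest figures to a settling rate are in Protocol 1.2: "the posterior mean response rate within the initial 6 hours of treatment was 62% in the retosiban group compared with 41% in the placebo group". Quiescence there meant 4 or fewer contractions per hour (close to 2 per 30 minutes) without cervical dilation change above 1 cm. The comparator was placebo. No atosiban figure is given.

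**Assumptions.**
- p = share settled by 6 h: 0.62 for retosiban; 0.41, 0.52 or 0.62 for the comparator.
- T = hour until which a non-settled woman is observed: 48, 12 or 8.
- s = share of later events still caught once continuous monitoring stops. Five 20-minute nonstress tests in the remaining 42 h cover 100/2520 = 0.04; higher values allow longer tests, extra tests and patterns that persist.
- True 48-h risk R = 10%, 30% or 50%, the same in both arms, with constant hazard L = −ln(1−R)/48.

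**Step 1: continuously monitored hours** = 6p + T(1−p), with T = 48.
- p = 0.62: 3.72 + 18.24 = 21.96 h.
- p = 0.41: 2.46 + 28.32 = 30.78 h; ratio 0.71.
- p = 0.52: 3.12 + 23.04 = 26.16 h; ratio 0.84.
- Equal p: ratio 1.00.

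**Step 2: share of women with a detected event**, with a = exp(−6L):

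(1−a) + a × [(1−p)(1 − exp(−(T−6)L)) + p(1 − exp(−42Ls))]

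Worked case, R = 30%, T = 48, s = 0.04: L = 0.3567/48 = 0.00743 and a = 0.956. The two later-detection terms are 0.268 (still on the monitor) and 0.0124 (off it).
- p = 0.62: 0.0436 + 0.956 × (0.38 × 0.268 + 0.62 × 0.0124) = 14.8%.
- p = 0.41: 0.0436 + 0.956 × (0.59 × 0.268 + 0.41 × 0.0124) = 20.0%.
- Ratio 0.74.

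Results for R = 30%, p = 0.62 against 0.41 (ratio in brackets):

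| Non-settled women observed until | s = 0.04 | s = 0.125 | s = 0.5 | s = 1 |
|---|---|---|---|---|
| 48 h | 14.8% v 20.0% (0.74) | 16.4% v 21.0% (0.78) | 22.7% v 25.2% (0.90) | 30.0% v 30.0% (1.00) |
| 12 h | 6.7% v 7.3% (0.91) | 8.2% v 8.3% (0.99) | 14.5% v 12.5% (1.16) | 21.8% v 17.3% (1.26) |
| 8 h | 5.6% v 5.7% (0.99) | 7.2% v 6.7% (1.07) | 13.5% v 10.9% (1.24) | 20.8% v 15.7% (1.32) |

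At T = 48 and s = 0.04 the ratio is 0.73 for R = 10% and 0.75 for R = 50%. With a comparator rate of 0.52 (R = 30%, T = 48) the ratios are 0.86, 0.88, 0.95 and 1.00 across the columns. With equal settling rates they are all 1.00.

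**Step 3: delivery tracings.** Suppose they independently flag a share d in both arms. The combined share is 1 − (1−x)(1−d). From 14.8% v 20.0%:
- d = 20%: 31.8% v 36.0%, ratio 0.88.
- d = 40%: 48.9% v 52.0%, ratio 0.94.
- d = 60%: 65.9% v 68.0%, ratio 0.97.

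**Step 4: a common window.** Over the first 6 h the detected share is 1 − exp(−6L): 1.3%, 4.4% and 8.3% for R = 10%, 30% and 50%, identical in both arms. The artefact disappears.

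**Step 5: Doppler.** Under Protocol 6.3.12.3, Category I needs moderate variability and no late or variable decelerations as well as a rate of 110 to 160. A normal Doppler rate supplies only the last of these.

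**The case against.** A reader might infer that the arm suppressing contractions better must look safer by construction. The documents do not support that.

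- Stopping is permitted, not required. It also needs a reassuring tracing, and nonstress tests follow at least every 8 hours.
- Delivery tracings also feed the special-interest count and do not depend on the stopping rule.
- Labor progression or delivery ends treatment (Protocol 4.4.2), so non-responders may leave early. The 8-hour and 12-hour rows above show that this can cancel or reverse the effect.
- The 41% is a placebo rate. Atosiban is an active tocolytic and its settling rate is not given.
- Fewer contractions may truly change tracings, so a lower percentage need not be artefact.

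A reader might also infer that Table 3.424 is distorted to the same degree. It is not, because its readings come mainly from vital-sign windows common to both arms. Some exposure remains. Readings are pooled by phase, dose-change and as-warranted readings are added, and SAP 8.2.6.2 does not say how several readings become one category, although SAP 11.5.1 gives mean, last-value and worst-value rules for different uses.

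Nor are Doppler readings wholly uninformative: tachycardia is a listed Category II example. SAP 8.2.6.2 also does not say that Doppler readings will be given a category; the point is that nothing excludes them.

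Finally, safety is descriptive and 97 women were enrolled. At about 48 per arm, 14.8% v 20.0% is roughly 7 v 10 women. All of this limits size and direction. None of it makes time observed independent of response.

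**Conclusion.** The special-interest percentages in Tables 3.171 and 3.172 can be distorted by unequal ascertainment, and nothing in either document corrects for it. The distortion may favour the arm that suppresses contractions better, but this is a risk and not a certainty. With no true difference, the illustrative ratios run from about 0.73 to above 1, and the ratio is 1 when settling rates are equal and follow-up is the same. These figures rest on assumed settling rates, nonstress-test yield, exit times and event risks, none of which the documents supply for this trial. Table 3.424 is affected to a smaller degree, and its post-treatment column may contain Doppler readings that cannot establish Category I. The consequence is for interpretation, not for a test. This is a cheap improvement.

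**What to change.** Monitoring itself does not change. In the SAP:

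1. Keep Tables 3.171 and 3.172, with a footnote that monitoring time depended on contraction response.
2. Add a between-arm display of Category II/III at the scheduled readings common to both arms: 15–30 minutes and 4–8 hours, with 20–24 hours and end of infusion shown as later readings. The denominator is the number of women with a category record at that time point. The 4–8 hour window runs past hour 6, when some women may already be off the monitor, so it is a common reading rather than guaranteed continuous monitoring. Use onset within the first 6 hours only if onset times are held; SAP 11.3.3 classifies adverse events by date.
3. Present Table 3.424 by scheduled time point, as SAP 8.2.6.1 does for maternal vital signs. Show dose-change, unscheduled and delivery readings separately.
4. At the post-infusion visit, categorise only cardiotocography readings. Report Doppler readings as a rate against the 110–160 bpm limits in SAP 11.8.3, with category not assessable.

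The cost is SAP wording and some extra programming on category records the protocol already collects. Step 4 needs the method of each reading to be identifiable. The downside is fewer events in the common-window comparison. A rate per monitored hour is not proposed, because neither document defines monitoring start and stop times as an analysis variable.
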